6.2.3 Follow Up Period and Trial Completion

A minimum of 28 days after the end of treatment all patients who started treatment are asked to come for a final follow up visit.

Follow up visit:

Assessments at this visit include:

- Physical examination and vital signs.
- •
- Urine sample for pregnancy test for women of childbearing potential.
- ECG.
- Review concomitant therapy and any adverse events.
- Spirometry.
- At the end of this visit the patient will have concluded their time in the trial.

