	possibility to reduce to two capsules tid (534 mg tid / 1602 mg daily) Day 16 three capsules in the morning only (801 mg, this is the last dose		

Boehringer Ingelheim BI Trial No.: 1199.229 c03463451-08

Trial Protocol Version 4.0

Page 5 of 118 Proprietary confidential information © 2016 Boehringer Ingelheim International GmbH or one or more of its affiliated companies

h			
Name of company:			
Boehringer Ingelheim	1		
Name of finished product:	:		
Ofev®			
Name of active ingredient	:		
Nintedanib			
Protocol date:	Trial number:		Revision date:
17 July 2015	1199.229		29 July 2016
	in the PK period)		
Mode of administration:	Ande of administration: Oral administration with food		
Duration of treatment:	16 days		
Endpoints	Pharmacokinetic Parameters:		
	Group 1:		
	Primary endpoints: AUC _{0-tz} and C _{max} of nintedanib		
	Secondary endpoin	ts: $AUC_{0-\infty}$ of nintedanib	
	Group 2:		
	Primary endpoints.	AUC and Cmar as of nirfenid	one
	1 mary enupoints. $100_{\tau,ss}$ and $C_{max,ss}$ of phreindone		
Safety criteria:	Incidence and intensity of adverse events, physical examination, vital		
	signs, ECG, change from baseline in laboratory parameters		
Statistical methods:	Descriptive statistics and analysis of variance (ANOVA) for AUC _{0-tz} ,		
	C_{max} and AUC _{0-∞} of nintedanib with and without the association with		
	pirfenidone (group	1) and for AUC _{τ,ss} and C _{max,ss} if	for pirfenidone with
	and without the ass	ociation with nintedanib (grou	p 2).

Page 6 of 118

63451-08Trial Protocol Version 4.0Page 6 ofProprietary confidential information © 2016 Boehringer Ingelheim International GmbH or one or more of its affiliated companies

FLOW CHART - GROUP 1

Trial Periods	Screening Period ¹	PK e	valuation	n Period ¹⁰	PK Follow-up Period ¹⁸
Visit	1	2	Phone call ⁶	3 ¹³	4
Weeks		0	2	311	7
Days	-28 to -1	1-2	15	23-24	52
Time window for visits			+	6 days	+3 days
Informed consent ²	Х				
Demographics	Х				
Medical history	Х				
Review of in-/exclusion criteria	Х	Х			
Drug and alcohol testing at site	Х	Х			
Physical examination	Х	Х		Х	Х
Vital signs ³	Х	Х		Х	Х
Laboratory tests	X			Х	Х
Pregnancy test (urine) ⁹	Х	Х		Х	Х
PK sample ⁷		X^{17}		X^{17}	
		Х			
		X ¹⁴		X^{14}	Х
		X^{14}		X^{14}	
12 lead-Electrocardiogram (ECG)	X				Х
Spirometry ¹²	X	Х		Х	Х
DLCO ¹⁹	X	$(X)^{19}$			
Register screening / start of treatment	X	Х			
Dispense trial drugs ⁴		X ¹⁷		Х	
Collect trial drug & compliance check				Х	
Dispense and/or collect & review diary ⁵		X^{17}		Х	

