1.2 DRUG PROFILE

1.2.1 Nintedanib

Nintedanib is a small molecule that inhibits a distinct spectrum of receptor tyrosine kinases (RTKs) and non-receptor tyrosine kinases (nRTKs) at pharmacologically relevant concentrations. Among them, FGFR (fibroblast growth factor/receptor), PDGFR (platelet derived growth factor/receptor) and VEGFR (vascular endothelial growth factor/receptor) have been implicated in IPF pathogenesis. Nintedanib binds competitively to the adenosine triphosphate (ATP) binding pocket of these receptors and blocks the intracellular signalling which is crucial for the proliferation, migration, and transformation of fibroblasts representing essential mechanisms of the IPF pathology [P08-08684; P14-02860].

A soft gelatine capsule formulation of nintedanib is used in humans. Nintedanib is absorbed moderately fast, with maximum plasma concentrations occurring between 2 - 4 hours after oral administration. Exposure to nintedanib increases in a dose proportional manner. The terminal half-life is in the range of 7 to 19 h and steady state is reached at the latest within one week of dosing. After food intake, a trend towards an increased systemic exposure (around 15 to 20%) and a delayed absorption was observed compared to administration under fasted conditions. Nintedanib is recommended to be taken with food. Nintedanib is preferentially distributed in plasma, with a blood to plasma ratio of 0.87. The absolute bioavailability of the capsule formulation of nintedanib was slightly below 5%. Nintedanib is mainly eliminated via faeces, with renal elimination playing a very minor role (0.7% of an orally administered radioactive dose).

Co-administration of nintedanib with the P-glycoprotein (P-gp) inhibitor ketoconazole increased exposure to nintedanib by 60-70% based on area under the curve (AUC) and by 80% based on a maximum measured concentration of the analyte in plasma (C_{max}) in a dedicated drug-drug

Boehringer IngelheimBI Trial No.: 1199.229c03463451-08Trial Protocol Version 4.0

Proprietary confidential information © 2016 Boehringer Ingelheim International GmbH or one or more of its affiliated companies

interaction (DDI) study. Patients taking potent P-gp inhibitors (e.g ketoconazole, erythromycin or cyclosporine) should be monitored closely for tolerability of nintedanib.

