1.2.2 Pirfenidone

The mechanism of action of pirfenidone in the treatment of IPF has not been established. After single oral-dose administration of 801 mg pirfenidone, C_{max} was achieved between 30 minutes and 4 hours (median time of 0.5 hours). Food decreased the rate and extent of absorption. Median t_{max} increased from 0.5 hours to 3 hours with food. Maximum plasma concentrations and AUC_{0-inf} decreased by approximately 49% and 16% with food, respectively. A reduced incidence of adverse reactions was observed in the fed group when compared to the fasted group. Pirfenidone was taken with food in controlled studies with IPF patients. The absolute bioavailability of pirfenidone has not been determined in humans. The mean terminal half-life is approximately 3 hours in healthy subjects and, as such, steady state accumulation is expected to be minimal. Pirfenidone is excreted predominantly in the urine (approximately 80% of the dose).

Pirfenidone is a substrate of cytochrome P450 1A2. Co-administration with the strong CYP1A2 inhibitor fluvoxamine increased exposure to pirfenidone by approximately 4-fold in non-smokers and 7-fold in smokers. Co-administration with ciprofloxacin (moderate inhibitor of CYP1A2) increased the exposure to pirfenidone by 81%. Agents or combinations of agents that are moderate or strong inhibitors of both CYP1A2 and one or more other CYP iso-enzymes involved in the metabolism of pirfenidone (i.e., CYP2C9, 2C19, 2D6, and 2E1) should be avoided during treatment with pirfenidone.

The efficacy of pirfenidone 2403 mg/day (3 capsules tid) was evaluated in patients with IPF in three phase III, randomized, double-blind, placebo-controlled, multi-centre trials (CAPACITY and ASCEND trials). The CAPACITY 2 trial showed a positive result on the primary endpoint of change from baseline in FVC % predicted at week 72, as well as on the secondary endpoint of progression-free survival (PFS). In the CAPACITY 1 trial there was no statistically significant difference at Week 72 for the primary endpoint. The ASCEND trial reported a positive result on the primary endpoint of change from baseline in FVC % predicted at week 52, as well as positive results on both key secondary endpoints of PFS and change from baseline in 6-minute walk test distance [R11-4827; R14-2103].

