5.3.4 Electrocardiogram

ECGs are to be conducted with site equipment as specified in flowchart 1 and flowchart 2. Changes should be examined, compared to previous test, and assessed for clinical relevance. Clinically relevant findings at Visit 1 will be recorded as baseline conditions, new abnormal findings thereafter will be recorded as adverse events.

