7.8.4 ECG

Not applicable, relevant ECG findings are recorded as baseline condition or AEs.

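### ECG is a named safety criterion, but no ECG is scheduled while patients take nintedanib or the combination; the only post-baseline tracing comes at least 28 days after the last dose.

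*Protocol*

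**What the plan says.** The safety criteria in the protocol synopsis include "ECG, change from baseline in laboratory parameters", alongside adverse events, physical examination and vital signs. Section 5.3.4 ties the timing to the flow charts: "ECGs are to be conducted with site equipment as specified in" the two charts. Clinically relevant findings at Visit 1 become baseline conditions, and new abnormalities after that become adverse events.

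The Group 1 flow chart marks the 12-lead ECG at Visit 1 and Visit 4 only. The visit lists agree. ECG appears in 6.2.1 (Visit 1) and 6.2.3 (follow-up), and in none of the legible 6.2.2 lists for Visits 2, 3, 3a or 3b. Vital signs, physical examination and spirometry are listed at every one of those visits. In the copy reviewed, the label of the matching Group 2 flow chart row is not legible. Its marks, at Visits 1 and 4, fit the visit lists.

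The follow-up visit is described in 6.2.3: "A minimum of 28 days after the end of treatment all patients who started treatment" are asked to come back for it.

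SAP 7.8.4 plans no ECG analysis: "Not applicable, relevant ECG findings are recorded as baseline condition or AEs".

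**The concern.** A safety measure can speak to a drug only if it is taken while the drug is present, or if the effect outlasts the drug. Here the two scheduled tracings fall before any trial medication and after full washout. A reversible change under nintedanib or under the combination would leave no trace in the scheduled ECGs.

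The protocol gives reasons to want such a reading. Section 1.2.1 reports a higher proportion of myocardial infarctions on nintedanib and asks for further observation. Section 3.3 says it is not known whether the two drugs together have additive adverse effects. Section 7.3.4 promises to compare safety data from screening, the course of the trial and the end of the trial with findings before treatment. For ECG, the schedule supplies nothing from the course of treatment.

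What is at stake is how the report reads. With ECG named as a safety criterion and no ECG-related adverse events listed, a reader could take the result as reassurance about the combination when no routine tracing was taken on it.

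**Working it through.** **Inputs**
- Last trial drug intake: Day 23 in Group 1 and Day 16 in Group 2 (flow charts and 6.2.2).
- Follow-up visit: at least 28 days after Day 24 in Group 1 and after Day 16 in Group 2 (6.2.2), with a window of +3 days (flow charts).
- Nintedanib (1.2.1): "The terminal half-life is in the range of 7 to 19 h".
- Pirfenidone (1.2.2): "The mean terminal half-life is approximately 3 hours in healthy subjects".
- Patients: 16 and 18 entered, with 12 evaluable per group after allowing for 4 and 6 dropouts (7.7).

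**Planned follow-up day**
- Group 1: 24 + 28 = Day 52. Group 2: 16 + 28 = Day 44. Both match the flow charts.
- Gap from last intake: Group 1, 52 − 23 = 29 days (32 at the end of the window). Group 2, 44 − 16 = 28 days (31 at the end of the window).

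**Washout at the shortest gap**
- 28 × 24 = 672 h.
- Half-lives elapsed = 672 / half-life. Nintedanib: 672/19 = 35.4 and 672/7 = 96. Pirfenidone: 672/3 = 224.
- Fraction remaining = 2 to the power of minus the number of half-lives. For nintedanib at 19 h this is about 2 × 10⁻¹¹; every other case is smaller.

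**Scheduled ECGs per patient, by drug on board**

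| Exposure | Group 1 | Group 2 |
|---|---|---|
| Nintedanib alone | 0 | not given alone |
| Combination | 0 | 0 |
| Pirfenidone alone | 0 | 1 (Visit 1, commercial supply) |

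The Group 2 entry follows from inclusion criterion 6 (3.6), which requires full-dose pirfenidone at entry, and from 4.1.4, which has the patient take commercial supply up to the day before Visit 2.

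**Labelling of a Visit 4 finding**
SAP 6.1 counts data up to and including 28 days after last intake as on-treatment. A finding first dated at the planned Group 2 visit (last intake + 28) is labelled on-treatment. The same finding at the planned Group 1 visit (last intake + 29) is not. In both cases the drugs have gone.

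**Yield of moving the tracing**
The target of evaluable patients is 12 + 12 = 24; the ceiling is 16 + 18 = 34. On-drug ECGs would rise from 0 to about 24 to 34 patients. A reading 3 to 4 h after the 08:00 dose coincides with scheduled PK draws at 11:00 and 12:00 in both groups (10.2). It also lies within the nintedanib peak range of 2 to 4 h (1.2.1) and near the fed median pirfenidone peak of 3 h (1.2.2).

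**The case against.** The strongest reply is that this is an exploratory PK interaction trial of two licensed drugs. Its safety analysis is descriptive, it has no ECG endpoint, and its adverse events of special interest are gastrointestinal perforation and hepatic injury. No primary or secondary result depends on an ECG. Section 1.2.1 also says that cardiac adverse events were balanced overall, that other ischaemic heart disease was less frequent on nintedanib, and that the meaning of the infarction finding is unknown. The discontinuation rule in 3.8.1 responds to signs or symptoms of ischaemia, not to a scheduled tracing. All of this stands, and it keeps the point modest.

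A reader might infer that the ECG data can say nothing about either drug, or that the SAP relies on the two scheduled tracings alone. The documents do not support that:
- In Group 2, Visit 1 is on pirfenidone and Visit 4 is off it. That contrast is crude, confounded with time and with the intervening nintedanib, and not planned for analysis, but it exists.
- Section 5.3.8 makes any clinically relevant ECG change reportable as an adverse event, SAP 7.8.4 does not restrict this to scheduled tracings, and nothing bars a symptom-driven ECG.
- A lasting change, such as that left by an infarction during treatment, could still appear at Visit 4.

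The remedy is also a trade. It gives up a routine end-of-trial ECG for one uncontrolled tracing on site equipment, with no pre-dose tracing that day. In Group 1 that tracing follows only a single nintedanib dose. Patients who do not reach seven stable days stop medication and have no PK samples (4.1.4), so those who tolerate treatment least would still have no on-drug ECG. This limits what the moved ECG can prove, but a tracing during exposure still tells more about exposure than one after 35 or more half-lives.

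**Conclusion.** The point holds in a bounded form. No ECG is scheduled under nintedanib or the combination, and the only scheduled post-baseline ECG follows complete washout. What is missing is a routine on-drug reading that could show a transient effect. The plan does not lack all ECG information.

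The washout conclusion rests on the half-lives in the protocol, the pirfenidone value being from healthy subjects. It is not sensitive to them: even the longest nintedanib value leaves more than 35 half-lives. The Group 2 schedule rests on the visit lists and on an unlabelled flow chart row that fits them. The figure of 24 to 34 patients assumes that the plan's own completion targets are met.

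The change is worth making because it is cheap and lets a stated safety criterion reflect exposure. It is a small gain in descriptive safety and alters no PK result.

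**What to change.** Move the post-baseline ECG from Visit 4 to the combination PK day: Visit 3 Day 23 in Group 1 and Visit 3b Day 16 in Group 2, about 3 to 4 h after the morning dose and just after a PK draw. Keep an ECG at Visit 4 only to follow up a finding from that tracing, or for patients who had no combination PK day. Amend both flow charts and sections 6.2.2 and 6.2.3.

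The cost is a few minutes on a busy sampling day and the loss of a routine end-of-trial ECG. The number of routine ECGs per patient and the equipment are unchanged, and the patient is already in clinic. Adding the tracing instead of moving it would keep the end-of-trial reading at the price of one extra ECG per patient.

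If the schedule can no longer change, state in SAP 7.8.4 and in the report that no scheduled ECG was taken on nintedanib or the combination, so that an absence of ECG findings is not read as reassurance. That costs one sentence in each.

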7. STATISTICAL METHODS AND DETERMINATION OF SAMPLE SIZE

7.1 STATISTICAL DESIGN - MODEL

The objectives of the current study are to investigate the effect of steady state pirfenidone on the pharmacokinetics of nintedanib and its metabolites following oral administration of 2403 mg/day pirfenidone and to investigate the effect of steady state nintedanib on the pharmacokinetics of pirfenidone at steady state following oral administration of 150 mg bid nintedanib.

This open-label, multiple-dose study consists of two groups. In total, 34 patients will participate in the trial, 16 patients in group 1 and 18 patients in group 2. Within each group, there will be a fixed sequence design: in group 1, a single oral dose of nintedanib of 150mg will be administered alone (reference treatment, R1) and in combination with 801mg tid pirfenidone (test treatment, T1; cf. Section 3.1) and in group 2, 7 days of 801mg tid pirfenidone will be administered alone (reference treatment, R2) and in combination with 7 days 150mg bid of nintedanib (test treatment, T2).

For each comparison between test and reference treatment, the statistical model used will be an ANOVA (analysis of variance) model on the logarithmic scale (see Section 7.3.1)

7.2 NULL AND ALTERNATIVE HYPOTHESES

For the comparisons described in Section 7.1, there is no hypothesis to be tested in a confirmatory sense. Instead, the ratios of adjusted geometric means (test/reference) for the primary PK endpoints and their two-sided 90% confidence intervals (CIs) will be provided.

7.3 PLANNED ANALYSES

The statistical analysis will be based on the following populations:

Treated Set:

The treated set consists of patients who receive at least one dose of study medication.

PK analysis set:

PK concentrations and parameters of a subject will be included in the analysis if they are not flagged for exclusion, e.g. due to PK non-evaluability or a protocol violation relevant to the evaluation of PK endpoints, which will be decided no later than in the Report Planning Meeting.

A PK concentration or parameter will be considered non-evaluable, if for example

- the subject experienced emesis that occurred at or before two times median t_{max} of the respective treatment for this treatment period (median t_{max} is to be determined excluding the subjects experiencing emesis),
- a pre-dose concentration is > 5% of the C_{max} value of that subject.

Relevant protocol violations may be for example

- Administered dose (amount of drug) is not in compliance with the protocol, i.e. is too low or too high
- Restricted medication use

Criteria for important protocol violations may be updated and more details will be provided in the TSAP.

The PK analysis set (PKS) includes all subjects in the treated set who provide at least one primary or secondary PK endpoint value not excluded according to the description above. Thus, a subject will be included in the PKS, even if he/she contributes only one PK endpoint value for one of the two PK days to the statistical assessment. The PKS will be used for the primary and secondary endpoint analyses.

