3.3 DISCUSSION OF TRIAL DESIGN, INCLUDING THE CHOICE OF CONTROL GROUP(S)

For relative bioavailability studies the intra-individual comparison design is viewed favorably due to its efficiency: since each subject serves as his own control, the comparison between treatments is based on a comparison within subjects rather than between subjects. This means that the inter-subject variability is removed from the comparison between treatments (cf. R94-1529). The design is expected to deliver valid results on the PK of a single oral dose of nintedanib with and without co-administration of pirfenidone at steady state (Group 1), as well as steady state pirfenidone with and without co-administration of nintedanib at steady state (Group 2). The current study design for Group 1 allows the perpetrator drug, pirfenidone, to reach a stable therapeutic dose, while minimizing the potential impact on nintedanib, the victim drug, which has previously shown a decrease in exposure upon co-administration with pirfenidone. Furthermore, as it is unknown whether there may be additive AEs when administering nintedanib and pirfenidone together, increasing the duration of concomitant administration of nintedanib and pirfenidone may elevate the potential for AEs unnecessarily. Therefore, the current study design for Group 1 minimizes both the risk of intolerability due to increasing AEs, as well as the risk of dropouts due to reduced drug efficacy, during coadministration of pirfenidone and nintedanib.

For Group 2, it is expected that there will already be patients stable on pirfenidone, as this drug is currently available for IPF in the UK. As such, using a steady state design for both the perpetrator (nintedanib) and the victim drug (pirfenidone) allows patients to remain at a stable therapeutic dose of pirfenidone, while reducing the likelihood of intolerability during an up-titration phase and, at the same time, reducing the likelihood of patients dropping out.

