The PK evaluation period for this group is for a minimum of 16 days plus 28 days follow-up and begins at Visit 2.

Visit 2 Day 1

- Review concomitant therapy and any adverse events since screening.
- A drug and alcohol test will be done at the clinic.
- Physical examination and vital signs.
- Urine pregnancy test for women of childbearing potential.
- Spirometry
- Reassessment of inclusion/exclusion criteria.
- •
- Registration of treatment start by emailing the form provided in the ISF to the sponsor.
- No PK samples are taken on this day.
- Dispense two wallets of pirfenidone and instruct the patient to take 801mg tid, the first dose should be given at the clinic with food and a glass of water.
- Provide patient with dosing instructions.
- Dispense diary.
- Remind patient of Visit 3a scheduled for Day 8.

Visit 3a Day 8

Once the patient has been on stable, full dose pirfenidone for 7 days (a 3 day window is allowed to ensure 7 consecutive days) they will return to clinic for the first PK day.

The patient should attend the clinic at approximately 07:00 so that the following assessments can be started before breakfast is given:

- Physical examination and vital signs.
- Urine pregnancy test for women of childbearing potential.
- Blood sample for laboratory tests (Section 5.3.3)

- Pre-dose PK samples should be taken according to PK Flowchart (Group 2, this should be taken prior to the other blood samples).

•

- Spirometry.
- Review concomitant therapy and any adverse events since previous visit and throughout the day at regular intervals.
- Patients will return all unused medication. Medication compliance will be assessed by counting returned (unused) capsules.
- The patient will return the diary card and this will be reviewed to check that the patient has received seven consecutive, stable days of treatment.
- Three 267 mg pirfenidone capsules should be given to the patient at 08:00 during breakfast (See PK Flowchart Group 2).
- PK samples should be taken according to PK Flowchart (Group 2).
- The patient should be given lunch at 12:00.
- Three 267 mg pirfenidone capsules will be given to the patient at 14:00 with a snack.
- After the PK time point at 14:00, the patient can leave the clinic.
- The patient should be given the remaining pirfenidone from the previous visit and also one new wallet of pirfenidone and one bottle of nintedanib to take home.

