- The patient should take the final dose of three 267 mg pirfenidone capsules at home at approximately 20:00 with food and a glass of water.
- The patient should be reminded to take pirfenidone and nintedanib from Day 9 at home for seven consecutive days.
- Remind patient of Visit 3b scheduled for Day 16.

Once the patient has received nintedanib and pirfenidone for 7 consecutive days, they will return to clinic for Visit 3b for the next PK day. If the patient needs to dose reduce the pirfenidone then this is allowed see Section 4.1.4.

Visit 3b Day 16

Once the patient has been on stable, pirfenidone and nintedanib for 7 days (a 3 day window is allowed to ensure 7 consecutive days) they will return to clinic for the next PK day.

The patient should attend the clinic at approximately 07:00 so that the following assessments can be started before breakfast is given:

- Physical examination and vital signs.
- Urine pregnancy test for women of childbearing potential.
- Blood sample for laboratory tests (Section 5.3.3)
- Predose PK samples should be taken according to PK Flowchart (Group 2, this should be taken prior to the other blood samples).
- •
- Spirometry.
- Review concomitant therapy and any adverse events since previous visit and throughout the day at regular intervals.

63451-08Trial Protocol Version 4.0Page 61 of 118Proprietary confidential information © 2016 Boehringer Ingelheim International GmbH or one or more of its affiliated companies

- Patients will return all unused medication. Medication compliance will be assessed by counting returned (unused) capsules.
- The patient will return the diary card and this will be reviewed to check that the patient has received seven consecutive, stable days of treatment.
- One 150mg nintedanib capsule and three 267 mg pirfenidone capsules should be given to the patient at 08:00 during breakfast (See section 10.2; this will be the last study medication that the patient will receive in the PK evaluation period of the trial).
- PK samples should be taken according to PK Flowchart (Group 2).
- The patient should be given lunch at 12:00.
- After the PK time point at 14:00, the patient can leave the clinic.
- No study drugs are given.
- Remind patient of PK FU visit scheduled for 28 days after this visit.

PK Follow-up/ End of Trial

The patient should return to the clinic 28 days or more after Visit 3b Day 16 for their PK Follow-up/ End of Trial Visit as detailed in section 6.2.3.

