6.3 PATIENT SETS ANALYSED

- **Screened set**

This patient set includes all patients having signed informed consent and performed visit 1.

- **Treated set (TS)**
 This patient set includes all patients who were dispensed study medication and were documented to have taken at least one dose of investigational treatment.

- **Pharmacokinetic analysis set (PKS)**
 The PKS will be used as defined in section 7.3 of the CTP.

The following table shows which patient set will be used for which study period and which class of endpoints.

Table 6.3: 1 Patient sets analysed

Class of endpoint	Patient set		
	Screened set	TS	PKS
Primary endpoint			X
Secondary endpoints			X
Further endpoints			X
Safety analyses		X	
Demographic/baseline characteristics / extent of exposure	X	X	

Note that the number of patients with available data for an endpoint may differ.

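### The rule that a pre-dose level above 5% of Cmax makes PK data non-evaluable is not limited to single-dose profiles, and as written it catches ordinary steady-state pirfenidone profiles in Group 2

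*Protocol*

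**What the plan says.** Protocol 7.3 sets out a single PK analysis set (PKS) for the whole trial. Its evaluability text opens with "A PK concentration or parameter will be considered non-evaluable, if for example" and then gives two cases. One is early emesis. The other is that "a pre-dose concentration is > 5% of the C_{max} value of that subject". No group, analyte or dosing state is named.

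The SAP does not narrow this. SAP 6.3 states: "The PKS will be used as defined in section 7.3 of the CTP". SAP 4 declares no departure from the protocol's methods. The violation table (SAP Table 6.2:1) does not mention pre-dose levels. SAP 7.4 describes the variables that carry exclusion flags and refers to internal PK standards for detail.

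The primary Group 2 endpoints are AUCτ,ss and Cmax,ss of pirfenidone (Protocol 5.1.1). Protocol 3.3 explains that Group 2 uses a steady-state design for both drugs, and Protocol 4.1.4 requires seven stable days of dosing before each of the two PK visits.

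**The concern.** A 5% pre-dose limit makes sense when the pre-dose level ought to be close to zero. That is so for the two single nintedanib doses in Group 1, where a higher level would point to carry-over or unrecorded intake. It does not hold for a drug sampled within a three-times-daily regimen, where the trough belongs to a normal profile.

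Two things depend on evaluability: which pirfenidone values enter the primary Group 2 comparison (Protocol 7.3 and 7.3.1), and when recruitment to the group stops, which happens once 12 evaluable patients have completed treatment (Protocol 3.4 and 7.7). If valid Group 2 profiles meet a listed ground for non-evaluability, the team must set the written rule aside to keep them. In an open-label trial that choice should not be left until concentrations have been seen. Applied to some patients and not others, the rule would tend to remove those who eliminate pirfenidone more slowly.

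**Working it through.** The 5% limit is a set rule with no derivation in the documents, so there is no planned figure to reproduce. The check is whether a typical Group 2 trough lies above it.

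**Inputs**
- Half-life: "The mean terminal half-life is approximately 3 hours in healthy subjects" (Protocol 1.2.2).
- Time to peak: "Median t_{max} increased from 0.5 hours to 3 hours with food" (Protocol 1.2.2). Trial doses are taken with food, so values towards 3 h are the more relevant; 0.5, 1, 2 and 3 h are all shown.
- Pre-dose sample: 07:00, before the 08:00 dose (Protocol 10.2).
- Evening dose: 20:00, an assumption. Protocol 6.2.2 gives that time for the evening after the Visit 3a profile, not for the evening before either PK day. The range 18:00 to 22:00 is shown.

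**Simple decay.** Treat the evening peak as equal to Cmax and let it decay to 07:00. With h the hours from evening dose to sample, trough/Cmax = 2^(−(h − tmax)/3). For a 20:00 dose h = 11, so tmax 3 h gives 2^(−8/3) = 15.7%.

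| Evening dose | h | tmax 0.5 h | 1 h | 2 h | 3 h |
|---|---|---|---|---|---|
| 18:00 | 13 | 5.6% | 6.2% | 7.9% | 9.9% |
| 20:00 | 11 | 8.8% | 9.9% | 12.5% | 15.7% |
| 22:00 | 9 | 14.0% | 15.7% | 19.8% | 25.0% |

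**Superposition.** A one-compartment oral model dosed at 08:00, 14:00 and 20:00 to steady state, half-life 3 h, takes the 07:00 value over the highest scheduled post-dose sample. It gives 11.1%, 13.1%, 19.8% and 33.5% for tmax 0.5, 1, 2 and 3 h. In this model the evening peak is 1.23, 1.24, 1.30 and 1.40 times the sampled morning Cmax, which is one reason why simple decay gives the lower, more cautious figures. The 33.5% needs an absorption half-life of 1.5 h and is best read as an upper value.

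**What would bring the typical trough down to 5%?** By simple decay, with log2(20) = 4.32:
- Break-even half-life with a 20:00 dose, (11 − tmax)/4.32: 2.43, 2.31, 2.08 and 1.85 h for the four tmax values, that is 19% to 38% shorter than 3 h.
- Break-even dose time at a 3 h half-life, tmax + 3 × 4.32 hours before 07:00: about 17:32, 17:02, 16:02 and 15:02.

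**Check of the proposed scope**
- Nintedanib in Group 2 (half-life 7 to 19 h, time to peak 2 to 4 h, Protocol 1.2.1): 11 h after a dose, 2^(−9/7) = 41% to 2^(−7/19) = 77% of the peak remains. It needs the same exemption.
- Nintedanib in Group 1: the pre-dose sample at 527 h is 527/19 = 27.7 half-lives after Day 1 even at 19 h, leaving 2^(−27.7), about 4.5 × 10⁻⁹. The rule does no harm there and keeps its purpose.

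**The case against.** The best counter-argument is that the rule was meant for single doses. Protocol 5.1.1 uses Cmax for single-dose nintedanib and Cmax,ss for steady-state pirfenidone. Protocol 7.3.1 and 7.7 keep that distinction, and the 5% rule says Cmax. This is real evidence of intent. It does not settle the reading, because Protocol 10.1 and the drug-profile sections use Cmax generically and the PKS definition serves both groups.

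Second, the criterion is given as an example, and nothing is excluded until a flag is set, no later than the Report Planning Meeting. Protocol 7.7 also allows extra patients if fewer than 12 have both PK assessments. This stands and limits the harm. But a listed case is described as one that will be considered non-evaluable, so discretion here means departing from the text. Adding patients would not help if their profiles met the same rule.

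Third, an internal PK standard may already contain the limit. That cannot be checked from the documents. SAP 7.4 applies the standard procedure only where the SAP has no specific definition, and SAP 6.3 supplies one by adopting Protocol 7.3. If the limit does exist, the gap is a missing cross-reference.

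Fourth, the text does not say which values are lost when the pre-dose level is high, and literal use would affect both PK days so visibly that it would be noticed. Both are fair. They argue against a large hidden bias, not against correcting the wording.

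**Conclusion.** The concern holds. Neither document limits the criterion, and on the protocol's own half-life a typical Group 2 pirfenidone trough is about 9% to 16% of Cmax by the cautious calculation and 11% to 33% by superposition, against a limit of 5%.

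The result rests on a healthy-subject mean half-life, an assumed evening dose time and, for the higher figures, a one-compartment model. With an 18:00 dose and the fasted time to peak the margin is small (5.6%). The documents give no spread of half-life and no value in IPF patients, so no number or share of affected patients is claimed.

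Because the team has discretion and the trial is exploratory, the practical harm is minor to moderate. It is still worth correcting, since the rule points the wrong way for the primary Group 2 data. Confidence is medium, mainly because the internal standards are not available.

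**What to change.** Add one sentence to SAP 6.3, for example: *The criterion of a pre-dose concentration above 5% of Cmax applies only to single-dose nintedanib profiles in Group 1; it does not apply to analytes at steady state (pirfenidone in either group, nintedanib in Group 2).* Record it in SAP 4 as a clarification of Protocol 7.3, and date it before concentrations are reviewed for flagging. If the internal PK standard already sets this limit, citing the clause in SAP 6.3 is enough.

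The cost is that sentence, one line in SAP 4 and one entry in the SAP history table. The protocol text can stay. No new evaluability criterion, data, patients or procedures are needed.
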